3.5.5.2 Pre-Discharge Assessment

Investigator will assess all subjects at the implant center prior to hospital discharge, or within 2-days post implant, whichever is shorter. Investigation team will:

- Assess for adverse events and deviations from investigation plan;
- Assess for changes in beta blockers, ACE, ARB, anti-coagulants, anti-platelets, anti-arrhythmics;
- Measure and record Aveir LP performance, as described in 3.5.3.3 LP Assessment and Programming;
- Assess magnet mode;
- Program Aveir LP per physician discretion;
- Obtain a 12-lead electrocardiogram (ECG) with pacing ON;
- Obtain a posterior/anterior (P/A) and lateral view chest x-ray to assess final LP position;
- Investigator will use medical judgment and provide institutional standard of care for post-pacemaker-implant monitoring.
- Collect medical billing information for implant

Data Submission

Complete and submit the following case report forms and device print outs to St. Jude Medical, Sylmar, CA using the EDC system.

- Pre-Discharge Form (includes medication changes)
- Aveir LP Assessment and Programming Form
- Healthcare Utilization Form
- EQ-5D patient survey
- Study Withdrawal Form, if applicable
- Adverse Event Form, if applicable
- Device Deficiency Form, if applicable
- Deviation Form, if applicable
- Product Out of Service Form, if applicable
- System Revision Form, if applicable
- Death Form, if applicable
- COVID-19 Assessment Log, if applicable

Clinical Investigation Plan for Europe

3.5.5.3 2-week and 6-week follow-up visits

All subjects will return to the investigation site for a 14-day and 42-day (± 7 days) follow-up visit. During this visit, investigation team will:

- Assess for adverse events and deviations from investigation plan;
- Assess for changes in beta blockers, ACE, ARB, anti-coagulants, anti-platelets, anti-arrhythmics;
- Measure and record LP performance, as described in 3.5.3.3 LP Assessment and Programming;
- Program Aveir LP and adjust programmable parameters of LP, as needed.
- 6 Minute Walk Test (6MWT)³
 - Administer 6MWT with rate-response feature in **VVIR ON** using the Rate Response Optimization function of the programmer (Refer to the 6 Minute Walk Test Protocol).
 - After completing 6MWT, use the Rate Response Optimization function of the programmer to model the response of the algorithm to the 6MWT protocol so that a peak sensor rate of approximately 100 beats/min is achieved. The results of this Rate Response Optimization are then used to adjust programmable sensor parameters of Aveir LP in preparation for the subsequent CAEP protocol.
- CAEP Protocol⁴
 - If the 6MWT is conducted the same day as the CAEP protocol, wait at least 1 hour after the 6MWT has been completed prior to starting the CAEP protocol.
 - The optimized sensor parameters resulting from the 6MWT are advised for the CAEP protocol, however, the physician has discretion to alter these parameters. Administer CAEP protocol with rate-response feature in **VVIR ON** mode (refer to CAEP protocol).
 - After completing the CAEP protocol, program Aveir LP and adjust programmable parameters of LP, as needed.

Data Submission

Complete and submit the following case report forms and device print outs to St. Jude Medical, Sylmar, CA using the EDC system.

³ Administration of the 6MWT can be done any time from the beginning of the 2-week follow-up visit, (until approximately 30 subjects contribute to the analysis).

⁴ Administration of the CAEP protocol can be done any time from the beginning of the 6-week follow-up visit, (until approximately 30 subjects contribute to the analysis).

Clinical Investigation Plan for Europe

- Follow-up Visit Form (includes medication changes)
- Aveir LP Assessment and Programming Form
- EQ-5D patient survey
- 6MWT Exercise Test Form, if applicable
- CAEP Exercise Test Form, if applicable
- Study Withdrawal Form, if applicable
- Adverse Event Form, if applicable
- Device Deficiency Form, if applicable
- Deviation Form, if applicable
- Product Out of Service Form, if applicable
- System Revision Form, if applicable
- Death Form, if applicable
- Healthcare Utilization Form, if applicable
- COVID-19 Assessment Log, if applicable

All source documentation associated with the 6MWT and CAEP, including device session printouts, source worksheets, and LP data files should be de-identified and submitted to the Sponsor.

3.5.5.4 3-Month Visit

All subjects will return to the investigation site for a 90-day (± 30 days) follow-up visit. During this visit, investigation team will:

- Assess for adverse events and deviations from investigation plan;
- Assess for changes in beta blockers, ACE, ARB, anti-coagulants, anti-platelets, anti-arrhythmics ;
- Measure and record Aveir LP performance, as described in 3.5.3.3 LP Assessment and Programming;
- Program Aveir LP and adjust programmable parameters of LP, as needed;

Data Submission

Complete and submit the following case report forms and device print outs to St. Jude Medical, Sylmar, CA using the EDC system.

- Follow-up Visit Form (includes medication changes)
- Aveir LP Assessment and Programming Form

Clinical Investigation Plan for Europe

- EQ-5D patient survey
- Medications, if any changes
- 6MWT Exercise Test Form, if applicable
- CAEP Exercise Test Form, if applicable
- Study Withdrawal Form, if applicable
- Adverse Event Form, if applicable
- Device Deficiency Form, if applicable
- Deviation Form, if applicable
- Product Out of Service Form, if applicable
- System Revision Form, if applicable
- Death Form, if applicable
- Healthcare Utilization Form, if applicable
- COVID-19 Assessment Log, if applicable

All source documentation associated with the 6MWT and CAEP, including device session printouts, source worksheets, and LP data files should be de-identified and submitted to the Sponsor.

3.5.5.5 6-Month Follow-up Visit

All subjects will return to the investigation site for a 180-day (± 30 days) follow-up visit. During this visit, investigation team will:

- Assess for adverse events and deviations from investigation plan;
- Assess for changes in beta blockers, ACE, ARB, anti-coagulants, anti-platelets, anti-arrhythmics;
- Measure and record Aveir LP performance, as described in 3.5.3.3 LP Assessment and Programming.

Data Submission

Complete and submit the following case report forms and device print outs to St. Jude Medical, Sylmar, CA using the EDC system.

- Follow-up Visit Form (includes medication changes)
- Aveir LP Assessment and Programming Form
- EQ-5D patient survey
- 6MWT Exercise Test Form, if applicable

Clinical Investigation Plan for Europe

- CAEP Exercise Test Form, if applicable
- Study Withdrawal Form, if applicable
- Adverse Event Form, if applicable
- Device Deficiency Form, if applicable
- Deviation Form, if applicable
- Product Out of Service Form, if applicable
- System Revision Form, if applicable
- Death Form, if applicable
- Healthcare Utilization Form, if applicable
- COVID-19 Assessment Log, if applicable

All source documentation associated with the 6MWT and CAEP, including device session printouts, source worksheets, and LP data files should be de-identified and submitted to the Sponsor.

3.5.5.6 12-Month Follow-up Visit and Each Follow-up Visit Every Subsequent 6-Months until Study Completion

All subjects will return to the investigation site for a 360-day visit (± 45 days) and every 180-days (± 45 days) follow-up visits. During these visits, investigation team will:

- Assess for adverse events and deviations from investigation plan;
- Assess for changes in beta blockers, ACE, ARB, anti-coagulants, anti-platelets, anti-arrhythmics;
- Measure and record Aveir LP performance, as described in 3.5.3.3 LP Assessment and Programming;
- Program Aveir LP and adjust programmable parameters of LP, as needed.

Data Submission

Complete and submit the following case report forms and device print outs to St. Jude Medical, Sylmar, CA using the EDC system.

- Follow-up Visit Form (includes medication changes)
- Aveir LP Assessment and Programming Form
- 6MWT Exercise Test Form, if applicable
- CAEP Exercise Test Form, if applicable
- Study Withdrawal Form, if applicable

Clinical Investigation Plan for Europe

- Adverse Event Form, if applicable
- Device Deficiency Form, if applicable
- Deviation Form, if applicable
- Product Out of Service Form, if applicable
- System Revision Form, if applicable
- Death Form, if applicable
- Healthcare Utilization Form, if applicable
- COVID-19 Assessment Log, if applicable

All source documentation associated with the 6MWT and CAEP, including device session printouts, source worksheets, and LP data files should be de-identified and submitted to the Sponsor.

3.5.5.7 Unscheduled Follow-up Visits

If a subject returns to the investigational site for a visit that is related to the device or implant procedure, the research team will:

- Assess for adverse events and deviations from investigation plan;
- Assess for changes in beta blockers, ACE, ARB, anti-coagulants, anti-platelets, anti-arrhythmics;
- As applicable, measure and record Aveir LP performance, as described in 3.5.3.3 LP Assessment and Programming;
- Program Aveir LP and adjust programmable parameters of LP, as needed.

Data Submission

Complete and submit the following case report forms and device print outs to St. Jude Medical, Sylmar, CA using the EDC system.

- Follow-up Visit Form (includes medication changes)
- Aveir LP Assessment and Programming Form
- 6MWT Exercise Test Form, if applicable
- CAEP Exercise Test Form, if applicable
- Study Withdrawal Form, if applicable
- Adverse Event Form, if applicable
- Device Deficiency Form, if applicable
- Deviation Form, if applicable

Clinical Investigation Plan for Europe

- Product Out of Service Form, if applicable
- System Revision Form, if applicable
- Death Form, if applicable
- Healthcare Utilization Form, if applicable
- COVID-19 Assessment Log, if applicable

All source documentation associated with the 6MWT and CAEP, including device session printouts, source worksheets, and LP data files should be de-identified and submitted to the Sponsor.

4.0 Hospitalizations

All hospitalizations, outpatient services, emergency room and urgent care visits that are related to heart failure, cardiac/ non-cardiac reasons and LP implant/retrieval/replacement procedure(s) must be reported to St. Jude Medical via a Healthcare Utilization Form within 10 working days of the center becoming aware of the subject's admission to the hospital. The investigation team will submit the Healthcare Utilization Form and supporting documentation (i.e., Admission/Discharge Summary) to St. Jude Medical, Sylmar, CA using the EDC system.

5.0 Protocol Deviations

Investigators are required to adhere to the investigation plan, signed Investigator's Agreement, applicable federal or state/local, laws and regulations, and any conditions required by the IRB/EC, or FDA/other country regulatory agencies.

A protocol deviation is used to describe situations in which the investigation plan was not followed. Investigator must report all deviations from the investigational to sponsor per 21 CFR §812.150. In addition, investigator must report all deviations to the reviewing IRB/EC per the IRB's/EC's reporting requirements.

Investigator must notify sponsor and the reviewing IRB/EC of any deviation from the investigation plan to protect the life or physical well-being of a subject in an emergency as soon as possible, but not later than 5-working days after the deviation has occurred, or no later than 5-working days after the investigator becomes aware of the deviation.

Clinical Investigation Plan for Europe

6.0 Adverse Events

To comply with worldwide standards and guidelines on clinical investigation adverse event reporting, the Sponsor has adopted uniform and worldwide applicable standard definitions and reporting timelines to be used and adhered to by the investigators.

A Clinical Events Committee (CEC) will review and adjudicate all Adverse Events. The CEC will base their final adjudication on the information provided on the case report forms, medical records, and their clinical knowledge and experience.

Investigator will document all AEs on the Adverse Event Form, including (at a minimum) a description of the event, date of onset, relationship to the investigational device, required interventions, duration, and outcome. Investigator will monitor all AEs until they are resolved, determined to be a chronic condition or the subject is lost to follow-up. Investigator will report all AEs regardless of whether it is anticipated or unanticipated and regardless of classification, seriousness, outcome or causality. Investigator will document AE relatedness to COVID-19 on the Adverse Event Form and may provide the assessments from any COVID-19 diagnoses/tests on the COVID-19 Assessment Log, as applicable.

Should an AE occur, complete an Adverse Event Form and submit to sponsor. If an adverse event occurs between scheduled visits, report the event as soon as possible without waiting until the next scheduled visit. Report the adverse event to the IRB/EC per the IRB/EC policy. Investigator will return any retrieved devices to sponsor for analysis.

Serious Adverse Event (SAE) Reporting

The investigator should report all SAEs to the Sponsor as soon as possible but no later than outlined below.

Clinical Site	Reporting timelines
All Sites	SAEs must be reported to the Sponsor no later than 3 calendar days from the day the site personnel became aware of the event or as per the investigative site's local requirements, if the requirement is more stringent than those outlined herein.

The date the site staff became aware of the event that met the criteria of an SAE, it must be recorded in the source document. The Investigator will further report the SAE to the local IRB/EC according to the institution's IRB/EC reporting requirements.

Clinical Investigation Plan for Europe

Unavoidable AEs are not reportable unless the condition worsens or continues beyond the time frame listed below. Unavoidable AEs, listed below, do not need to be reported if they are resolved within the time frame specified.

Table 5: Unavoidable AEs related to the Implant Procedure

Event	Time Frame post-Implant
Anesthesia related nausea/vomiting	<24 hours
Low-grade fever (<100 degree Fahrenheit fever or < 37.8 degree Celsius	< 48 hours
Percutaneous access pain	< 72 hours
Mild to moderate bruising/ecchymosis at percutaneous access site	< 72 hours
Sleep problems (insomnia)	< 72 hours
Back pain related to laying on the table	< 72 hours

If an **UNANTICIPATED (SERIOUS) ADVERSE DEVICE EFFECT** occurs, Sponsor requires the investigator to report any UADE/USADE to the Sponsor as soon as possible [21 CFR 812.150 (a) (1)], but within 3 calendar days [Sponsor's requirement] of the investigator's knowledge of the event, unless local requirements are more stringent, and to the IRB/ECs per IRB/EC requirements. Sponsor will take any steps necessary to investigate the event and will be responsible for notifying FDA and all other participating IRBs/ECs and investigators.

Should sponsor determine, either through physician reports or in-house testing, that an unanticipated adverse event presents an unreasonable risk to participating subjects, sponsor will suspend the clinical investigation and notify all participating investigators, IRBs/ECs and FDA.

Clinical Investigation Plan for Europe

Table 6: List of foreseeable adverse events and anticipated adverse device effects

*Access site bleeding event	
Air embolism	Intermittent capture
Angina pectoris	Interruption of desired pacemaker function due to electrical interference, either electromyogenic or electromagnetic
Arterial puncture	Keloid formation
AV fistula	Loss of normal device function due to battery failure or component malfunction
Bladder puncture	Muscle and nerve stimulation
Blood transfusion	Myocardial damage
Blunted or poor sensor response	Myocardial infarction
Body rejection phenomena	Myocardial irritability
Bowel penetration	Oversensing
Cardiac arrhythmias	Pacemaker syndrome
Cardiac dissection	Palpitations
Cardiac perforation	Pericardial effusion or rub
Cardiac tamponade	Pericarditis
Chronic nerve damage	Phrenic nerve/diaphragmatic stimulation
Damage to vessels	Pneumothorax/Hemothorax
Death	Premature battery depletion
Device dislodgment	Programmer/software anomaly
Dizziness	Pseudoaneurysm formation
Dyspnea	Psoas abscess
Embolism	Reaction to contrast
Endocarditis	Septic arthritis
Excessive Bleeding	Seroma
Exit block	Syncope
Failure to capture/loss of capture	Threshold elevation
Femoral nerve injury with resulting paresthesias	Thromboemboli
Heart Failure	Thrombosis
Hematoma formation, including retroperitoneal hematoma/hemorrhage	Undersensing
High impedance	Valve damage
Inability to interrogate or program due to programmer or device malfunction	Venous occlusion

Clinical Investigation Plan for Europe

Inability to disengage snare from docking button	
Induced ventricular ectopy or arrhythmias	Venous perforation
Infection, local at access site, or systemic	Ventricular ectopy
Insufficient cardiac output	Ventricular tachycardia

***Access site bleeding event is defined in section 3.5.5.1.**

A right ventriculogram carries risk, most notably, allergic reaction to contrast media.

6.1 Device Deficiencies/Malfunctions

Sites should report all device deficiencies/malfunctions on the appropriate CRF form.

The investigator must report all device deficiencies/malfunctions to the Sponsor as soon as possible but no later than outlined below.

Clinical Sites	Reporting timelines
All Sites	Sites must report device deficiencies/malfunctions to the Sponsor no later than 3 calendar days from the day the site personnel became aware of the event or as per the investigative site's local requirements, if the requirement is more stringent than those outlined.

Sites must report device deficiencies/malfunctions to the IRB/EC per the investigative site's local requirements.

Sites should return the device, if not implanted or not remaining in the subject, to the Sponsor.

6.2 Adverse Event Reporting to Country Regulatory Authorities by the Sponsor

The Sponsor will report SAEs and reportable device deficiencies/malfunctions to the country regulatory authority, per local requirements.

Clinical Investigation Plan for Europe

Contact details are provided below:

Note: Reportable device deficiencies/malfunctions include device deficiencies/malfunctions that might have led to an SAE if a) suitable action had not been taken or b) intervention had not been made or c) if circumstances had been less fortunate. These are handled under the SAE reporting system.

7.0 Deaths

All subject deaths that occur during this study must be reported to St. Jude Medical within 3 calendar days of the center being notified (Refer to SAE Reporting in Section 6.0). Notification of a death should include a detailed statement of the pertinent events and be signed by the investigator in addition to the completion of the appropriate forms (Death form, Withdrawal form, and Product Out of Service form) and submitted to St. Jude Medical, Sylmar, CA using the EDC system. It is the investigator's responsibility to notify the IRB/EC per the IRB/EC policy.

- Date and time of death
- Place death occurred (e.g. hospital, nursing home, subject's home)
- If death was witnessed
- Identification of the rhythm at the time of death, if known (include any available documentation)
- Cause of death
- Any other circumstances surrounding the death
- Approximate time interval to death from the initiating event
- Autopsy report (if performed)
- Whether it was device and/or procedure related
- Whether it was related to the study

If any of the above information is not available, investigator will provide an explanation in the death narrative of what attempts (and how many) were made to obtain the information, and the outcome of those attempts. At a minimum, investigator will place two (2) phone calls, followed by a certified letter, to the subject's next of kin and provide clinical notes and witness statements. If possible, interrogate the pacemaker. Retrieve and print all episode diagnostics, and programmed parameters. If applicable, the pacemaker should then be programmed

Clinical Investigation Plan for Europe

OFF. Attempt to explant the pacemaker and return any explanted devices to sponsor for analysis promptly. Clearly state on Case Report Form the reason the pacemaker is not being returned to sponsor.

8.0 Committees and Core Laboratories

8.1 Data and safety monitoring board (DSMB)

Sponsor will establish an independent DSMB to review safety data. The DSMB will consist of at least 3 members with study-related backgrounds. Members will include at least one statistician and two cardiologists with pacemaker experience. St. Jude Medical will appoint members of the DSMB and the chairperson. St. Jude Medical may provide administrative support to DSMB meetings, but will not be a voting member and will not be present during closed portions of the meeting. Non-DSMB members are not allowed to be present during DSMB closed meetings. Refer to the DSMB Charter.

Sponsor will provide to FDA/other country regulatory agency within 10 working days of receipt copies of written communication from the DSMB that relates to safety concerns, or changes to the study plan, procedures or informed consent document. Sponsor will provide the DSMB within 10 working days copies of any letter from FDA or other country regulatory agency that relates to safety concerns, or changes to the study plan, procedures or informed consent document.

8.2 Clinical events committee (CEC)

Sponsor will establish an independent CEC to review all adverse events. The CEC's role is to determine relationship of event to device and or procedure. The CEC will consist of at least 3 members with study-related backgrounds. Members will include cardiologists with pacemaker experience. St. Jude Medical will appoint members of the CEC and the chairperson. St. Jude Medical may supply study information and provide administrative support for CEC meetings, but will not be a voting member. Refer to the CEC Charter.

9.0 Withdrawals

Withdrawal is defined as termination of a subject's participation from the clinical trial. All reasonable efforts should be made to retain the subject in the clinical trial until completion of the clinical trial. All reasons for withdrawal will be documented. Reasons for withdrawal include, but are not limited to the following:

- Subject Death
- Subject and/or Family Request representing withdrawal of consent

Clinical Investigation Plan for Europe

- Subject Lost to Follow-Up: Subject will be considered “lost to follow-up” after a minimum of 2 documented phone calls by personnel at the investigational center to the subject or emergency contact, a certified letter is sent to the last known address and two consecutive visits pass without the investigator receiving data.
- Subject Participation terminated by investigator based on the best medical interest of the study subject
- LP explanted and not reimplanted
- Unsuccessful Implant.
- LP abandoned and Aveir LP not re-implanted

A subject’s participation in any clinical investigation is voluntary and the subject has the right to withdraw at any time without penalty or loss of benefit. Sites must notify the Sponsor of the reason(s) for subject discontinuation. A Withdrawal Form will be completed and submitted to St. Jude Medical, Sylmar, CA using the EDC system. Investigators must also report this to their respective IRB/EC as defined by their institution’s procedure(s).

No additional follow-up is required or data recorded from subjects once withdrawn from the clinical investigation, except for the status (deceased/alive if subject agrees). If the subject had an adverse event, the investigator will monitor all adverse events until they are resolved, if possible, or determined to be a chronic condition.

However, if a subject withdraws from the investigation due to problems related to the safety or performance of the device under investigation, the investigator shall ask for the subject's permission to follow his/her status/condition outside of the clinical investigation. The investigator may continue to assess for adverse events and interrogate and/or program the LP at his/her discretion in order to continue to evaluate the subject’s health and the LP’s performance.

In case of subject withdrawal of consent, the site should make attempts to schedule the subject for a final clinical investigation visit. At this final follow-up visit, the subject will undergo the following assessments:

- Assess for adverse events and deviations from investigation plan
- Assess for changes in beta blockers, ACE, ARB, anti-coagulants, anti-platelets, anti-arrhythmics
- As applicable, measure and record Aveir LP performance, as described in LP 3.5.3.3 LP Assessment and Programming
- Program Aveir LP and adjust programmable parameters of LP, as needed.

Clinical Investigation Plan for Europe

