#### 3.3 Subject Early Termination

Subject early termination reasons including deaths, withdrawals, lost-to-follow-up, etc. will be summarized descriptively for subjects terminated in the enrolled population.

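### Loss to follow-up is handled as terminal withdrawal and can be declared from day 49, which ends data collection well before the 12-month endpoints with no stated way back

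*Protocol*

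**What the plan says.** CIP section 9.0 lists loss to follow-up among the reasons for withdrawal. Three conditions must all be met. Two are contact attempts: the label applies "after a minimum of 2 documented phone calls by personnel at the investigational center to the subject or emergency contact, a certified letter is sent". The third concerns attendance, and requires that "two consecutive visits pass without the investigator receiving data".

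The same section sets the consequence. "Withdrawal is defined as termination of a subject's participation from the clinical trial", and "No additional follow-up is required or data recorded from subjects once withdrawn from the clinical investigation". Two exceptions apply to every withdrawn subject: vital status, if the subject agrees, and monitoring of adverse events the subject already had. Two further provisions are narrower. Continued follow-up outside the study is for subjects who withdraw because of device safety or performance problems, and the final visit is for subjects who withdraw consent. Neither covers a lost subject.

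Section 9.0 also states a general duty: "All reasonable efforts should be made to retain the subject in the clinical trial until completion of the clinical trial".

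Visit timing is in CIP Table 4 and sections 3.5.5.3 to 3.5.5.6, counted from successful implant (CIP 3.1). Early visits are close together, with a "14-day and 42-day (± 7 days) follow-up visit". Later ones are far apart, with a "360-day visit (± 45 days) and every 180-days (± 45 days) follow-up visits".

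Both confirmatory endpoints are read at 12 months. SAP 2.3.1 counts qualifying safety events up to day 360, and SAP 2.3.2 uses the pacing threshold and R-wave amplitude at the 12-month visit.

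**The concern.** A rule that counts missed visits acts quickly where visits are dense. Here the dense part of the schedule is the first six weeks, and the endpoints are read about a year after implant. A subject who skips two early visits and does not answer can be closed out while the implant is in place and most of the endpoint period lies ahead.

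Missing two early visits is not the same as being unobtainable at month 12. The subject may have been away, ill or in hospital elsewhere. If that person attends again at month 5, section 9.0 has already ended participation and says that data are no longer recorded. The 12-month measurement and any complication after termination are then missing because of the rule, not because they could not be obtained. In a single-arm study tested against fixed performance goals, endpoint data that could have been collected should not be given up.

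**Working it through.** The documents state no day on which a subject becomes classifiable as lost, so there is no plan figure to reproduce. The days follow from the visit windows.

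**Inputs**
- Windows, in days after implant (CIP Table 4): 2-week 14 ± 7; 6-week 42 ± 7; 3-month 90 ± 30; 6-month 180 ± 30; 12-month 360 ± 45; then every 180 ± 45.
- Missed-visit condition: two consecutive visits without data (CIP 9.0).
- Endpoint time: day 360 (SAP 2.3.1), and the 12-month visit (SAP 2.3.2).

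**Formula.** Earliest day on which the missed-visit condition is met = target day of the second missed visit + its upper window.

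| Visits missed | Earliest day | Days before day 360 | Days before the 12-month window closes (day 405) |
|---|---|---|---|
| 2-week and 6-week | 42 + 7 = 49 | 360 − 49 = 311 | 405 − 49 = 356 |
| 6-week and 3-month | 90 + 30 = 120 | 360 − 120 = 240 | 405 − 120 = 285 |
| 3-month and 6-month | 180 + 30 = 210 | 360 − 210 = 150 | 405 − 210 = 195 |
| 6-month and 12-month | 360 + 45 = 405 | after day 360 | 0 |
| 12-month and 18-month | 540 + 45 = 585 | after day 360 | after the window |

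These are earliest days. Classification also needs the two calls and the letter, for which section 9.0 sets neither a start nor a deadline. Nothing visible prevents them from being complete by day 49. The pre-discharge assessment is not counted as a visit here because it is done at the implant centre before the subject goes home.

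**What each row means for the endpoints.** In the first three rows termination comes before the 12-month window opens on day 360 − 45 = 315. A returning subject could still have given a 12-month measurement, and complications between termination and day 360 could still have been counted. In the last two rows the 12-month window has already closed, so the classification takes no endpoint data away.

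**Is there a way back?** Of the provisions in section 9.0, vital status gives neither a device measurement nor a complication. Monitoring of adverse events concerns events the subject already had, and CIP 6.0 allows that monitoring to stop at loss to follow-up. The other two clauses are for other kinds of withdrawal. No visible text reopens participation for a subject classed as lost.

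**The case against.** The strongest reply is that the rule is stricter than a count of missed visits. Two calls and a certified letter are required as a minimum, and the general duty to retain subjects has no condition on visit number. A careful site would keep trying and would not rush to close a record on day 49. That is fair: day 49 is what the text permits, not what will usually happen. But the retention duty does not undo the specific rule. Once a subject is classed as lost, section 9.0 ends participation and stops recording, and it says nothing about reappearance.

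A reader might also infer harm at the other end of the schedule: someone who attends month 6 and then disappears cannot be classed as lost until day 585. The documents do not support endpoint damage there. Safety events count to day 360 and the 12-month window closes on day 405, so a label applied later changes neither. Until then the subject remains in the study and data can still be recovered. If the 6-month visit was missed too, the relevant day is 405. Whether the loss counts under SAP 3.3 would be incomplete at the analysis cannot be judged, because the timing section (SAP 2.6) is redacted.

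Nor can it be said that the vital-status exception is unusable for someone out of contact. Agreement may have been obtained at enrolment, and the consent form is not available for review.

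**Conclusion.** The point holds for early loss to follow-up. The text allows a subject with an implanted LP to be terminated from day 49, 120 or 210, which is 311, 240 or 150 days before day 360, and provides no return. This conflicts with the section's own aim of retaining subjects to completion. It rests on the Table 4 windows and on the contact attempts being finished by those days.

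The number of subjects affected is unknown. The documents give no loss rate, and SAP 2.8 on missing data is redacted. A reader might try to express the effect as a probability of meeting the 80% effectiveness goal, but that would measure the assumptions and not this rule. Assume 200 implanted subjects, 90% true success and an exact one-sided 2.5% test. With nobody missing, the bar is 172 successes and the probability of passing is 97.3%. With 10 missing and counted as failures it falls to about 46%. With the same 10 dropped, the bar is 163 of 190 and it is 97.6%. Nor are those 10 tied to early classification; they could equally be deaths or withdrawn consents.

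This is therefore a cheap improvement that avoids needless loss of endpoint data, not a threat to the trial's conclusions that can be demonstrated from the documents.

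**What to change.** Amend CIP section 9.0 as follows.

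1. Separate missed-visit status from withdrawal, so that missing visits changes a subject's tracking status but does not end participation.
2. Start the calls and the certified letter when any single visit window closes without data.
3. Do not withdraw a subject as lost to follow-up before the 12-month window closes on day 405, unless the subject withdraws consent.
4. State that a subject who returns before then resumes follow-up, with 12-month device data, adverse events and vital status recorded.

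The cost is protocol wording, a few more contact attempts, and some unresponsive subjects kept open in the database until day 405. Hypotheses, sample size and treatment do not change.
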